9.4.9. Handling of Missing Data

All efforts will be made to minimize the occurrence of missing data. It is not expected that dropout rates will differ between groups. Therefore, the primary method of handling missing efficacy data in the ITT analysis set will be based on last observation carried forward (LOCF).

Other imputation methods (e.g., MMRM) may be used as a sensitivity analysis to the LOCF method.

All safety analyses will be conducted using the safety analysis set. No imputations will be made for missing safety data.

Additional details on imputation and sensitivity analyses are provided in the SAP.

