6.1.3 Visit Windowing

Data will be summarized based on nominal visit indications with the exception of data captured at early termination and unscheduled visits. Data from early termination and unscheduled visits will be summarized based on mapped visit values. The analysis windows for early termination and unscheduled visits are presented in the following table.

Analysis Windows

Scheduled Visit	Target Study Day	Window (Days)
Day 14	15	9 to 21
Day 28	29	22 to 42
Day 56	57	43 to 70
Day 84	85	71 to 98

Data collected at early termination and unscheduled visits prior to study day 9 will not be analyzed, with the exception of those identified as baseline values. Data collected at early termination and unscheduled visits after study day 98 will not be included in analyses.

The definition for the study day included in each study window is defined as below:

Study Day prior to Day 1 = Visit Date – Day 1 Date

Study Day on or after Day 1 = Visit Date – Day 1 Date + 1

If an assessment's mapped visit is a visit at which the subject has data from a scheduled visit present, or if no analyses are planned for the assessment at the mapped visit, the data collected at the early termination or unscheduled visit will not be included in analyses.

In the event of multiple values from unscheduled or early termination assessments within an analysis window, the value closest to the scheduled visit target study day will be used for analyses. If two values tie as closest to the time point (for example, one value is before and the other value is after the time point), then the later value will be selected.

Data collected at all visits will be included in the data listings with visit presented as reported by the site.

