6.1.5 Handling of Dropouts or Missing Data

All efforts will be made to minimize the occurrence of missing data. It is not expected that dropout rates will differ between groups. Therefore, the primary method of handling missing efficacy data in the ITT analysis set will be based on last observation carried forward (LOCF). Summary of efficacy and pharmacology variables for the PP subjects will be based on available data. No imputation will be done for non-efficacy related variables.

If a partial date is reported where the day is missing, then the day will be imputed as the first day of the month unless the month is the same month as the first application of study drug then the day will be that of first application with the month and year remaining the same. If a partial date is reported where the month is missing, then the month will be imputed to January unless the year is the same year as the first application of study drug then the month will be that of first application with the year remaining the same. If a partial date where both the day and month is missing, follow details as stated previously.

Missing AE start dates will be imputed using partial date imputation rules as previously described in this Section.

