6.8 Analysis of Efficacy

The efficacy analyses will be performed using the ITT (primary) and PP (supportive) analysis sets. The lesion count and IGA analyses will employ the methods for handling missing data as described by Section 6.1.5. Lesion count and IGA data will also be shown in by-subject listings.

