SD	xx.xx	xx.xx	xx.xx	xx.xx	xx.xx	xx.xx	
Median	xx.x	xx.x	xx.x	xx.x	xx.x	xx.x	
Min., Max.	xx, xx	xx, xx	xx, xx	xx, xx	xx, xx	xx, xx	
LSMean ^a			xx.x	xx.x	xx.x	xx.x	0.xxxx ^b
LSSD ^a			xx.xx	xx.xx	xx.xx	xx.xx	
Unranked P-value vs. Combined Vehicle ^a				0.xxxx	0.xxxx	0.xxxx	
Ranked P-value vs. Combined Vehicle ^c				0.xxxx	0.xxxx	0.xxxx	

^a Least squares mean, standard deviation, and contrast p-values from an analysis of covariance with factors of treatment group (vehicle treatment groups included as single combined treatment group) and corresponding baseline lesion count as the covariate.

^b Skewness test is based on methods presented by J.H. Zar (1984).

^c Contrast p-values from a ranked analysis of covariance with factors of treatment group (vehicle treatment groups included as single combined treatment group) and corresponding baseline lesion count as the covariate.

Note: Missing values imputed using LOCF.

SOURCE: USERNAME\SPONSOR\PROJECT\JOBNAME (DATE,TIME)

Repeat Table 14.2.1.1 for the following:

Table 14.2.1.2: Primary Efficacy Endpoint: Summary of Absolute Change from Baseline in Inflammatory Lesion Count at Day 84 (PP Population)

Programming note: replace last footnote with:

Note: No imputations were made for missing data.

Table 14.2.1.3: Sensitivity Analysis of Primary Efficacy Endpoint: Summary of Absolute Change from Baseline in Inflammatory Lesion Count at Day 84 (ITT Population)

Repeated Measures Analysis on Observed Data	Vehicle QD (N=xx)	Vehicle BID (N=xx)	Vehicle Combined (N=xx)	BTX 1503 5% BID (N=xx)	BTX 1503 5% QD (N=xx)	BTX 1503 2.5% QD (N=xx)
Change from Baseline in Inflammatory Lesion Counts						
n	xx	xx	xx	xx	xx	xx
Mean	xx.x	xx.x	xx.x	xx.x	xx.x	xx.x
SD	xx.xx	xx.xx	xx.xx	xx.xx	xx.xx	xx.xx
Median	xx.x	xx.x	xx.x	xx.x	xx.x	xx.x
Min., Max.	xx, xx	xx, xx	xx, xx	xx, xx	xx, xx	xx, xx
LSMean ^a			xx.x	xx.x	xx.x	xx.x
LSSD ^a			xx.xx	xx.xx	xx.xx	xx.xx
P-value vs. Combined Vehicle ^a				0.xxxx	0.xxxx	0.xxxx

^a Least squares mean, standard deviation, and contrast p-values from a repeated measures analysis of covariance with factors of treatment group (vehicle treatment groups included as single combined treatment group), visit, treatment by visit interaction, and corresponding baseline lesion count as the covariate. Note: No imputations were made for missing data.

SOURCE: USERNAME\SPONSOR\PROJECT\JOBNAME (DATE,TIME)

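### Read literally, SAP 6.1.3 can remove a subject's last lesion count before LOCF is applied, so an older count is carried to Day 84 in the primary ITT analysis (minor)

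*SAP*

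**What the plan says.** SAP 6.1.3 sets analysis windows for ET and unscheduled visits: study days 9 to 21 (Day 14), 22 to 42 (Day 28), 43 to 70 (Day 56) and 71 to 98 (Day 84). Where an assessment's "mapped visit is a visit at which the subject has data from a scheduled visit present", the rule is that "the data collected at the early termination or unscheduled visit will not be included in analyses". A separate sentence sets a lower limit: "Data collected at early termination and unscheduled visits prior to study day 9 will not be analyzed", baseline values excepted. The dropped values remain visible, because "Data collected at all visits will be included in the data listings with visit presented as reported by the site".

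SAP 6.8 links the efficacy analyses to the missing-data section: "The lesion count and IGA analyses will employ the methods for handling missing data as described by Section 6.1.5". For ITT efficacy data, SAP 6.1.5 says only that "the primary method of handling missing efficacy data in the ITT analysis set will be based on last observation carried forward (LOCF"). The shell for the primary ITT table (Table 14.2.1.1) adds nothing beyond "Note: Missing values imputed using LOCF". Protocol 9.4.9 does not fill the gap, since it points back: "Additional details on imputation and sensitivity analyses are provided in the SAP".

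**The concern.** LOCF needs a definition of the last observation. The SAP does not give one, and its only rule on which counts may enter analyses removes some late counts. Where that rule applies, the value analysed as Day 84 in the primary endpoint is not the last count the subject gave, even though a later one was collected and is listed.

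Two things are at stake. The primary dataset may rest on older information than the trial holds. And two programmers working from the same SAP could build different primary datasets, depending on whether they apply the exclusion before or after carrying forward.

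**Working it through.** The plan gives no figure on this point to reproduce. The check is a reading of the text, followed by a count of calendar days.

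**1. Does anything exempt LOCF?**
- SAP 6.1.3: excluded counts do not enter analyses. No exception for imputation.
- SAP 6.1.5: names LOCF. No rule on eligible counts.
- SAP 6.8 and the Table 14.2.1.1 note: refer to 6.1.5 and to LOCF. No exception.
- Protocol 9.4.9: leaves the detail to the SAP.

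No exemption is stated.

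**2. One subject.** Scheduled counts on study days 14 and 28, an ET count on study day 40, nothing later.
- Day 40 lies in 22 to 42, so it maps to Day 28.
- Day 28 already has a scheduled count, so the day-40 count is excluded.
- Day 84 is missing, and the latest count left is from day 28. It is carried.
- Age difference: 40 − 28 = 12 days.

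**3. Which ET days are affected?** Assume every earlier scheduled visit was attended. A count is dropped if it falls after the scheduled visit but inside that visit's window. Days dropped per window = window end − visit day.
- Visits on 14, 28, 56: (21 − 14) + (42 − 28) + (70 − 56) = 7 + 14 + 14 = 35, namely study days 15–21, 29–42 and 57–70. Largest age difference: 14 days.
- Earliest visits the protocol allows (11, 23, 51): 10 + 19 + 19 = 48. Largest difference: 19 days.
- Latest allowed (17, 33, 61): 4 + 9 + 9 = 22. Largest difference: 9 days.
- SAP target days (15, 29, 57): 6 + 13 + 13 = 32. Largest difference: 13 days.

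The base is study days 9 to 83, that is 83 − 9 + 1 = 75 days. Days 2 to 8 are left out because the separate lower limit already bars them. The illustration is therefore 35 of 75 days, with a range of 22 to 48 across the protocol visit windows.

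**4. Do the other analyses recover the count?**
- Repeated-measures analysis (SAP 6.9, shell headed Table 14.2.1.3): observed data by visit under the same window assignment. The Day 28 slot holds the scheduled count, so the day-40 count is absent.
- Per-protocol analysis (SAP 6.1.5): available data with no imputation. The day-40 count is not a Day 84 value, so it does not enter there either.

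**The case against.** **The rule is about summaries.** SAP 6.1.3 opens with how data are to be summarised, so one can argue that it does not reach imputation. But the sentence that excludes the count speaks of analyses, and the section does not limit that word to by-visit tables. What stands is that some readers will take it this way, which is a reason to clarify.

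**The literal rule is workable.** It gives one answer, is applied without regard to treatment, and could be defended as a convention: assign counts to visits, let scheduled data take precedence, then carry forward. That is fair. Its cost is that a later count already in hand is set aside, under a method named for the last observation.

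**Few subjects can be affected.** Protocol 5.3.1 and 7.3.7 steer end-of-study assessments to day 84 (±5 days) where possible, and a count taken then is kept. Table 3 schedules no other extra visits. This narrows the group but does not empty it. Protocol 7.3.7 covers terminations for reasons other than an AE, Protocol 5.3.1 also asks for the assessments before the subject withdraws, and the SAP itself provides ET windows from study day 9.

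**Other analyses exist.** The repeated-measures and per-protocol results do show whether conclusions depend on carried values in general. They do not show the effect of this rule.

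**The trial is exploratory.** Protocol 9.4.8 and SAP 6.1.8 say so, and Protocol 9.2 says that a non-significant result is not a failed study. This stands and keeps the severity low.

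**Conclusion.** The point holds as a minor defect of specification. On its literal wording the SAP carries an older count to Day 84 in the primary ITT analysis when (a) the subject has no count in the Day 84 window and (b) the last count falls in a window that already holds a scheduled count.

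A reader might infer two stronger things, and the documents support neither.
- *That 35 of 75 means nearly half of early terminators lose their last count.* These are calendar days, counted on the assumption that all earlier visits were attended on days 14, 28 and 56. The documents give no dropout rate and no distribution of ET timing, so the number of subjects is unknown.
- *That the primary comparison is biased for or against the active arms.* The rule takes no account of treatment, and nothing shows whether the dropped counts would be higher or lower than the carried ones, or whether this differs by arm. Size and direction cannot be computed.

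**What to change.** Before unblinding, amend SAP 6.1.3 and 6.1.5 to say:

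1. The same-window exclusion applies only to by-visit summaries of observed data.
2. For LOCF, the value carried to a missing visit is the latest post-baseline count collected from study day 9 up to the end of that visit's analysis window (study day 21, 42, 70 or 98). ET and unscheduled counts not assigned to a visit are eligible.
3. A count from a later nominal visit is never used. This is needed because the ITT tables for Days 14, 28 and 56 also use LOCF.
4. The existing bar on ET and unscheduled counts before study day 9 stays.
5. The report gives, by arm, how many subjects' carried Day 84 value differs between the two rules.

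Two cases check the wording. With counts on days 14, 28 and 40 (ET), the day-40 count goes to Days 56 and 84. With counts on days 14, 56 and 84 and Day 28 missed, the Day 28 value is the day-14 count, so nothing is carried backward.

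The cost is a few sentences and a small programming change on data already collected.

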If a subject is deemed eligible, they may be enrolled and begin Baseline assessments (within 35 days after the Screening Visit). Assessments for safety (CBC, chemistry, and urinalysis) will be obtained at the Baseline Visit (Day 1). If the Screening and Baseline Visits are not conducted on the same day, lesion counts, IGA, UDS, and a review of concomitant medications will be repeated. A UPT for WOCBP will be repeated if greater than 7 days from the Screening Visit. Baseline photographs of the face (selected sites) will be obtained. The Acne-QoL will be administered. Clinical site staff will apply the first dose of study drug. Cutaneous tolerability assessments will be conducted prior to and approximately 15 minutes after the first application. Subjects will be given a diary and sufficient study drug to last until their Day 28 Visit and instructed in the proper application to cover their entire face.

Subjects will return to the clinic on Day 14 for a review of their diary to ensure compliance with study drug applications. Lesion counts, IGA and cutaneous tolerability assessments will be conducted. In addition, the subject will apply study drug during the visit for the clinical site to confirm correct application techniques. AEs and concomitant medications will be reviewed.

Subjects will return to the clinic on Day 28 and Day 56 for cutaneous tolerability assessments, UPT, lesion counts and IGA. Subjects will also be queried for AEs and changes in concomitant medications. Diaries and study drug will be returned and reviewed for compliance. In addition, the subject will apply study drug during the visit for the clinical site to confirm correct application techniques. Study drug will be dispensed along with the diary for the next 28 days of study drug treatment.

Subjects will return to the clinic for their final visit on Day 84 for safety, tolerability and efficacy assessments, including lesion counts and IGA scoring of facial acne. Safety labs (CBC, chemistry, and urinalysis) and a UPT for WOCBP will be obtained. Photographs of the face will be obtained at selected sites. Cutaneous tolerability assessments will be conducted, and concomitant medications and AEs will be reviewed. The Acne-QoL and a patient reported outcome (PRO) will be administered at Day 84, assessing the subject's perception of the change

| | |

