5.3. Subject Withdrawal or Termination

5.3.1. Reasons for Withdrawal or Termination

If a subject is withdrawn from the study, the subject's enrollment in the study will terminate and study drug application will be discontinued. Efforts will be made to perform all assessments scheduled for the Day 84 Visit prior to subject withdrawal. The Day 84 Visit should be scheduled for day 84 (± 5 days), if possible.

A subject may be withdrawn from further study participation under the following circumstances:

- At the subject's request.

- Noncompliance with protocol by the subject as determined by the study site staff and investigator.
- Adverse Event (decision to be removed from study made by either the investigator or subject). The investigator must notify the sponsor immediately if a subject is withdrawn because of an AE.
- Pregnancy.
- Decision by the investigator or sponsor that termination is in the subject's best medical interest or for an administrative decision for a reason other than that of an AE.
- Lost to follow-up, as determined by failure to respond to at least 2 telephone calls followed by certified letter sent to the subject's last known address. All attempts to contact the subject must be documented in the subject's source documents.
- Sponsor decision to halt the entire study.

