6.1.8. Duration of Therapy

Subjects will apply study drug for 84 days with a final application on Day 84. Subjects receiving BID dosing will apply 167 doses and subjects receiving QD dosing will apply 84 doses.

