6.4.4 Per-Protocol (PP) Population

All subjects in the ITT population who complete the Day 84 visit without noteworthy study protocol violations will be included in the PP population and analyzed according to the treatment group received. The PP population will include subjects in the ITT population who do not meet any of the following criteria:

- Violated the inclusion/exclusion criteria;
- Have taken any interfering concomitant medication;
- Did not complete both IGA and lesion count efficacy assessments at the Day 84 visit;
- Have missed both the Day 28 and Day 56 visits;
- Have not been compliant with the dosing regimen (i.e. subjects must apply 80-120% of the expected applications of study medication during participation in the study);
- Out of visit window at the Day 84 visit by ± 5 days;

Subjects that discontinue from the study due to an AE related to study treatment or documented lack of treatment effect will be included in the PP population. Prior to breaking the blind, other

additional criteria may be added to the list to accommodate for unforeseen events that occurred during the conduct of the trial that result in noteworthy study protocol violations.

All efficacy analyses will be performed on the PP population.

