The total number of applications expected for QD subjects is as follows:

$\text{Date Subject Ended Participation} - \text{Date of Randomization} + 1$.

If the total number of applications for BID subjects exceeds 178 then it will be set to 178.

If the total number of applications for QD subjects exceeds 89 then it will be set to 89.

Compliance will be calculated as a percentage as 100 times the total number of applications taken divided by the total number of applications expected while enrolled in the study.

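### SAP 6.1.3 sets visit targets (study days 15, 29, 57, 85) one day later than the protocol's Days 14, 28, 56 and 84; the direct effect is small, but it leaves the per-protocol Day 84 window open to two readings

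*SAP*

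**What the plan says.** **Protocol.** The Baseline visit, at which the first dose is applied, is Day 1 (protocol summary; Table 3 in section 7.3.8). Section 6.1.8 fixes the end of treatment: "Subjects will apply study drug for 84 days with a final application on Day 84". It also gives the dose totals: "Subjects receiving BID dosing will apply 167 doses and subjects receiving QD dosing will apply 84 doses". The final visit is Day 84 ± 5 days (sections 7.3.6 and 7.3.8). Section 5.3.1 uses the same day for withdrawn subjects: "The Day 84 Visit should be scheduled for day 84".

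**SAP day numbering and windows.** Section 6.1.3 uses the same origin. Its formula begins "Study Day on or after Day 1 = Visit Date", then subtracts the Day 1 date and adds 1. Its table gives these targets and windows:

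| Visit | Target study day | Window |
|---|---|---|
| Day 14 | 15 | 9–21 |
| Day 28 | 29 | 22–42 |
| Day 56 | 57 | 43–70 |
| Day 84 | 85 | 71–98 |

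The table applies only to early-termination and unscheduled visits. All other data keep their nominal visit, and an unscheduled or early-termination value is dropped if the subject has scheduled data at the visit it maps to. Where several such values share a window, "the value closest to the scheduled visit target study day will be used for analyses", and a tie goes to the later value.

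**SAP per-protocol set.** One exclusion in section 6.4.4 is "Out of visit window at the Day 84 visit" by ± 5 days. No central day is named and section 6.1.3 is not cited. Table 14.0.2 repeats the ± 5 days, also without a centre.

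**SAP exposure caps.** Section 6.10.1 states: "If the total number of applications for QD subjects exceeds 89 then it will be set to 89". The cap for twice-daily subjects is 178.

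**The concern.** With the same Day 1 in both documents, a visit called Day 84 should have target study day 84. The SAP gives 85, and the three earlier targets are shifted by one day in the same way. Two things depend on this.

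- **Which count is analysed.** The closest-to-target rule uses the target directly, so a one-day shift can change the lesion count or IGA that stands for a visit.
- **Who is per-protocol.** The ± 5 day criterion needs a centre. A programmer looking for one could take 85 from section 6.1.3. The per-protocol set supports the primary analysis and is the only set used for the SAP's subset analyses (section 6.1.11).

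**Working it through.** **1. Which study day is the protocol's Day 84?** Inputs: the dose totals in protocol 6.1.8 (84 and 167) and the counting rule in SAP 6.10.1, under which twice-daily subjects have two applications on the first day and one on the last.

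- Once daily: doses = last day − 1 + 1. Last day 84 gives 84; last day 85 gives 85.
- Twice daily: doses = 2 × (last day − 1) + 1. Last day 84 gives 2 × 83 + 1 = 167; last day 85 gives 2 × 84 + 1 = 169.

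Only last day 84 reproduces the protocol's figures. The protocol's Day 84 is therefore study day 84 on the SAP's formula, and target 85 is one day late. The offsets at the other visits are 15 − 14, 29 − 28 and 57 − 56, each +1.

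**2. The SAP's exposure caps.** 84 + 5 = 89 and 2 × 89 = 178 match both caps. 85 + 5 = 90 and 2 × 90 = 180 match neither.

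**3. Effect on the selected value.** Take two values on study days a < b in one window, with target t and ties to the later value. The later value is selected when b − t ≤ t − a, that is, when a + b ≤ 2t.

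- Target 84: later value if a + b ≤ 168.
- Target 85: later value if a + b ≤ 170.

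The choices differ only when a + b is 169 or 170, and then target 85 takes the later value where target 84 takes the earlier. The window 71–98 has 28 days, so 28 × 27 / 2 = 378 pairs. Sum 169 occurs for 14 pairs (71 and 98 through 84 and 85) and sum 170 for 13 (72 and 98 through 84 and 86), a total of 27.

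Example: counts on days 82 and 87 (sum 169). From 84 the distances are 2 and 3, so day 82 is used. From 85 they are 3 and 2, so day 87 is used.

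| Window | Sums at which the choice differs | Pairs affected |
|---|---|---|
| Day 14 (9–21) | 29, 30 | 12 of 78 |
| Day 28 (22–42) | 57, 58 | 14 of 210 |
| Day 56 (43–70) | 113, 114 | 27 of 378 |
| Day 84 (71–98) | 169, 170 | 27 of 378 |

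These are counts of possible pairs, not probabilities. The documents do not say how often such pairs occur.

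**4. Effect on the per-protocol window.** 84 ± 5 is study days 79–89; 85 ± 5 is 80–90. Only day 79 (inside the first, outside the second) and day 90 (the reverse) differ.

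**5. Do the window limits need to move?** Midpoints between targets 14, 28, 56 and 84 are 21, 42 and 70. The limits 9–21, 22–42, 43–70 and 71–98 still hold, with each midpoint day going to the earlier visit.

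**The case against.** The strongest reply is that the table hardly matters. It does not govern scheduled visits. The closest-to-target rule operates only when there is no scheduled value at the visit and at least two other values fall in its window, and the protocol schedules no extra lesion counts. This stands, and it is why the point is minor.

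A reader might go further and infer that the SAP misclassifies per-protocol subjects. For example, if Day 84 visits were normally distributed around day 84 or 85 with an SD of 2 or 3 days, 1.2% to 5.2% would fall on day 79 or 90, or about 4 to 19 of 360. The documents do not support that as a finding. Section 6.4.4 does not centre the window on 85, SAP 4.1 lists the return visits as Days 14, 28, 56 and 84, and SAP 4.1.1 refers to the protocol schedule, which has Day 84 ± 5. The plain reading is therefore 79–89. The spread is also assumed, and the figure takes every randomised subject to attend Day 84 and meet all other criteria. What remains is an ambiguity: the criterion has no stated centre, and the one numeric target study day in the SAP disagrees with the protocol.

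It can also be said that 15, 29, 57 and 85 are exactly 14, 28, 56 and 84 days after first dose, and that 9–21 is 15 ± 6, so elapsed time may have been intended. That may explain the numbers, but the SAP does not say so, and the protocol's dose totals show that its own Day 84 is not elapsed day 84.

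Finally, the caps limit applications and do not define a visit window. With one application on the last day, a twice-daily subject ending on day 89 would reach 2 × 88 + 1 = 177, not 178. The caps are consistent with 84 + 5 but do not prove it; the dose totals carry the argument.

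**Conclusion.** The one-day offset is real at all four visits and follows from the documents alone. Its direct effect is limited to subjects with no scheduled value at a visit and two or more unscheduled or early-termination values in its window; for two values in the Day 84 window, it acts in 27 of 378 possible pairs. If last observation carried forward draws on mapped values, which the SAP does not state, a different choice in an earlier window could also reach a dropout's Day 84 value. Scheduled counts, and so most primary-endpoint data, are unaffected.

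The per-protocol effect is conditional. It arises only if 85 is taken as the centre of the ± 5 days, and then only for visits on study days 79 and 90. The number of subjects is unknown because the documents give no visit timing. Severity is minor.

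**What to change.** In the SAP 6.1.3 table, change the target study days to 14, 28, 56 and 84 so that they agree with the protocol. The four windows can stay; the first then runs from 5 days before its target to 7 days after, which does not affect the selection rule. In SAP 6.4.4 and Table 14.0.2, state the per-protocol criterion as a Day 84 visit on study days 79 to 89, which is the protocol's own window. The cost is four numbers, one sentence and one table label. Make the change before unblinding, so that neither the selected counts nor per-protocol membership has to be settled with treatment known.
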